5.1.13.6 PAC-QOL Questionnaire

The PAC-QOL questionnaire¹³ (**Appendix I**) will be used to assess patient quality of life. The PAC-QOL questionnaire is a 28-item self-report instrument designed to evaluate the burden of constipation on patient's everyday functioning and well being in the 2 weeks (14 days) prior to assessment. Each item is rated on a 5-point Likert scale ranging from 0 (not at all) to 4 (extremely). Development of the PAC-QOL items was informed by both clinician and patient focus groups and the primary validation study evaluated use of the PAC-QOL in the US, Netherlands, Belgium, Canada, and Australia using French and Dutch translations in addition to the original English language based instrument.¹³ This questionnaire takes approximately 5 minutes to complete. The instrument can be used to generate an overall score, but is also reported to assess 4 specific constipation-related domains, including: 1) worries and concerns (11 items), 2) physical discomfort (4 items), 3) psychosocial discomfort (8 items), and 4) satisfaction (5 items). The PAC-QOL is validated for a **2-week recall**, therefore, participants will be asked to complete this questionnaire every 14 days during the initial and crossover treatment periods, every 28 days during the optional extension phase and at the end of study visit. This questionnaire takes approximately 5 minutes to complete.

5.1.13.7 Brief Pain Inventory-Short Form (BPI-sf)

The Brief Pain Inventory (BPI) is one of the most widely used measurement tools for assessing clinical pain. The BPI allows patients to rate the severity of their pain and the degree to which their pain interferes with common dimensions of feeling and function. The BPI is available in two formats: the BPI-Short Form (BPI-sf), which is used for clinical trials, and the BPI-Long Form, which contains additional descriptive items that may be clinically useful. For the purposes of this study, we will use the BPI-sf, a 9 item self-administered questionnaire used to evaluate the severity of a patient's pain and the impact of this pain on the patient's daily functioning (**Appendix J**). The patient is asked to rate their worst, least, average, and current pain intensity, list current treatments and their perceived effectiveness, and rate the degree that pain interferes with general activity, mood, walking ability, normal work, relations with other persons, sleep, and enjoyment of life on a 10 point scale. The BPI-sf is validated for **24-hour recall**. Participants will be asked to complete this questionnaire daily during the initial and crossover treatment periods, every 28 days during the optional extension phase, and at the end of study visit. This questionnaire takes approximately 5 minutes to complete.

5.2 Screening/Baseline Procedures

Assessments performed exclusively to determine eligibility for this study will be done only after obtaining informed consent. Assessments performed for clinical indications (not exclusively to determine study eligibility) may be used for baseline values even if the studies were done before informed consent was obtained.

All screening procedures must be performed within 21 days prior to initiation of study treatment unless otherwise stated. The screening procedures include:

- Written informed consent
- Review of inclusion and exclusion criteria
- Complete medical/surgical/OIC history

- OIC Confirmation (see Section 5.1.4)
- Demographics
- Documentation of concomitant medications
- Complete physical examination, including vital signs, weight and height
- ECOG performance status assessment
- Complete blood count with differential and platelets
- Comprehensive metabolic panel
- Serum or urine pregnancy test (*within 72 hours of Study Day 1*) for females of child-bearing potential (see inclusion/exclusion criteria)
- PAC-SYM
- PAC-QOL
- BPI-sf
- BSS

Following confirmation of all eligibility criteria, subjects will be randomized in a 1:1 ratio to either Arm A or Arm B. Randomization will occur within 3 days of the initial treatment phase.

5.3 Procedures During Initial Treatment and Crossover Treatment Phases

During the initial and crossover treatment phases of the study, physical exam, ECOG performance status, vitals, weight, and laboratory tests will be performed on the first day of each treatment period. Thereafter, these procedures will be performed according to routine frequency for the participant's oncology care. If these procedures are performed as part of routine oncology care, results will be collected for the study.

5.3.1 Day 1, Day 18

- Documentation of concomitant medications, adverse events and serious adverse events
- ECOG performance status assessment
- Physical exam, vital signs, and weight
- Complete blood count with differential and platelets
- Comprehensive metabolic panel
- Naloxegol dispensing (*Arm A, Day 1 only; Arm B, Day 18 only*)
- Naloxegol administration (*Arm A, Day 1; Arm B, Day 18*)
- Patient study drug diary (*Arm A, Day 1; Arm B, Day 18*)
- PAC-SYM
- PAC-QOL
- BPI-sf
- BSS
- Patient medication use diary
- Patient bowel movement diary

5.3.2 Days 2-7, Days 9-14, Days 19-24 and Days 26-31

- Documentation of concomitant medications, adverse events and serious adverse events
- Naloxegol administration (*Arm A, initial period only; Arm B crossover period only*)
- Patient study drug diary (*Arm A, initial period only; Arm B crossover period only*)
- BPI-sf
- BSS

- Patient medication use diary
- Patient bowel movement diary

5.3.3 Day 8, Day 25

- Documentation of concomitant medications, adverse events and serious adverse events
- Naloxegol administration (*Arm A, initial period only; Arm B crossover period only*)
- Naloxegol pill count (*Arm A, initial period only; Arm B crossover period only, via phone if in-person visit not conducted*)
- Patient study drug pill diary (*Arm A, initial period only; Arm B crossover period only*)
- PAC-SYM
- BPI-sf
- BSS
- Patient medication use diary
- Patient bowel movement diary

5.4 Procedures During Optional Extension Phase (up to 12-weeks)

Physical exam, ECOG performance status, vitals, weight, and laboratory tests will be performed at the start of the optional extension phase, on Day 32. Thereafter, these procedures will be performed according to routine frequency for the participant's oncology care. If these procedures are performed as part of routine oncology care, results will be collected for the study.

5.4.1 Days 32-116 (Daily)

- Documentation of concomitant medications, adverse events and serious adverse events
- ECOG performance status assessment (*Day 32 only*)
- Physical exam, vital signs, weight (*Day 32 only*)
- Complete blood count with differential and platelets (*Day 32 only*)
- Comprehensive metabolic panel (*Day 32 only*)
- Naloxegol dispensing (*Day 32 only*)
- Naloxegol administration
- Patient study drug diary

5.4.2 Days 32, 39, 46, 53, 60, 67, 74, 81, 88, 95, 102, 109 (Weekly)

In addition to daily assessments listed in Section 5.5.1, the following will be performed:

- Naloxegol pill count (*via phone if in-person visit not conducted*)
- PAC-SYM (*Days 32, 60, 88 only*)
- PAC-QOL (*Days 32, 60, 88 only*)
- BPI-sf (*Days 32, 60, 88 only*)

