Cross-Over	Usual Care: stimulant laxative ± osmotic laxative	Single 25 mg tablet Route: Orally, on an empty stomach 1 hour before breakfast or 2 hours after first meal of the day	Daily, Days 18-31	2 weeks (14 days)
Extension (Optional)	Single 25 mg tablet Route: Orally, on an empty stomach 1 hour before breakfast or 2 hours after first meal of the day	Single 25 mg tablet Route: Orally, on an empty stomach 1 hour before breakfast or 2 hours after first meal of the day	Daily, Days 32-116	12 weeks (84 days)

Wash out: Based on an elimination half-life of 10 hours, a 3-day washout period (50 hours or 5 half lives, approximately 48 hours) will occur before crossover.

Optional 12-week extension: Patients on Arms A and B will have the option to continue on naloxegol at 25 mg daily for an additional 12-week extension phase upon completion of initial and crossover treatment phases.

On Study Days 1, 18, 32, patients will undergo physical exam with vital signs and weight, ECOG performance status, complete blood count, comprehensive metabolic panel, and will receive a new treatment supply. Pill counts and study drug accountability will also be performed.

During initial and crossover treatment periods, patients will complete daily questionnaires and diaries, including the patient study drug diary, patient bowel movement diary, patient medication use diary, BSS, and BPI-sf. Concomitant medications and adverse event data will also be collected daily. All adverse events will be graded according to NCI CTCAE v4.03. Weekly assessments will include patient completion of the PAC-SYM questionnaire. Bi-weekly assessments include patient completion of the PAC-QOL questionnaire. Pill counts will be performed weekly throughout the duration of study, and may be performed via telephone call by a member of the study team if no in-person visit has occurred with the patient during a previous week.

During the optional extension phase, patients will be asked to return to clinic every 28 days for a new supply of naloxegol, return of any unused naloxegol, review of the previous month's study drug diary, pill count and completion of PAC-SYM, PAC-QOL, and BPI-sf. Concomitant medications and adverse event data will continue to be collected daily.

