5.0 STUDY PROCEDURES

Refer to the study **Schedule of Events** for assessments to be performed.

All patients will be closely monitored for safety and tolerability throughout treatment and at the completion of study treatment.

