8.1.2 Drug Accountability/Subject Compliance

Records of study medications used, dosages administered, and intervals between visits will be kept during the study. Subjects will be asked to fill out a daily study drug diary while taking naloxegol and bring with them, along with any unused study drug, when they return to clinic every 14 days during the initial and crossover treatment phases, and at each in-person visit during the optional extension phase. A review of the subject-completed study drug diary and pill count will be performed by a member of the study team at each of these visits. In addition, a study team member will contact the patient weekly via telephone to perform pill counts if no in-person visit has occurred with the patient during a previous week.

Final drug accountability will be noted at the completion of the trial. Patients will be asked to return all unused medication at the end of the study.

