10.4 Data Collection and Management

Records and data to be obtained from the study subjects are detailed above in the **Schedule of Events**. Subject outcome information will be documented in the electronic medical record and subject's research record. Data for this study will be entered into a password-protected set of electronic case report forms via the Velos eResearch web-based system. Velos eResearch is an integrated software system for managing clinical trials. This system supports several clinical trial functions, including electronic case report forms, tracking and scheduling of subject visits and events, and study reporting. The software links to the UCSD Health System's EPIC Electronic Medical Record System to provide improved information and integration for clinical research projects. A robust support team assists investigators in implementing protocols and calendars and building electronic case report forms. Velos provides automated data export procedures for designated users into Excel, and then transferred into R. Access to the Velos database for this study will be limited to those users required to perform study-specific functions such as data entry and monitoring. A designated study coordinator from the UCSD Moores Cancer Center Clinical Trials Office will be responsible for entering all study data.

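### PAC-QOL is promised every 14 days, but the schedule gives patients who decline the extension no form covering the crossover period

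*Combined protocol and SAP*

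**What the plan says.** The narrative sections promise a regular form for everyone. Section 4.1 states: "Bi-weekly assessments include patient completion of the PAC-QOL questionnaire". Section 5.1.13.6 states that "participants will be asked to complete this questionnaire every 14 days during the initial and crossover treatment periods", and gives the instrument a 14-day recall.

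The operational lists differ. The Schedule of Events marks PAC-QOL at screening, Day 1, Day 18, the extension (footnote 8, every 28 days at drug refill) and End of Study. Section 5.3 agrees: PAC-QOL appears under "5.3.1 Day 1, Day 18" but not in Sections 5.3.2 or 5.3.3, which cover the other treatment days. The Day 32 form appears only in the extension list of Section 5.4.2: "PAC-QOL (*Days 32, 60, 88 only".

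Staff are sent to the schedule twice. Section 5.0 says: "Refer to the study Schedule of Events for assessments to be performed". Section 10.4 says: "Records and data to be obtained from the study subjects are detailed above in the" Schedule of Events.

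End of Study timing is given in two ways: 28 ± 7 days after the last study treatment in the Schedule of Events, and within 28 days in Sections 4.1, 4.8 and 5.5.

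Section 6.4 places quality of life in the first 4 weeks of study treatment, which Sections 2.4 and 6.2 explain as the initial and crossover phases. A crossover value is therefore intended. Section 9.3.3 compares treatments with a mixed model containing treatment and period, but does not say which form supplies each period's PAC-QOL. Section 9.2.1 requires baseline and follow-up data for secondary analyses and gives no other method for missing data.

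**The concern.** On the schedule as written, the only form that recalls the whole crossover period is completed only by patients who choose more naloxegol. Section 2.4 defines that choice as the patient's preference for the drug, so whether a crossover score exists may depend on how the patient did on naloxegol compared with usual care.

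The selection would work in the same direction in both arms. Arm B patients who did poorly on naloxegol would tend to lose their naloxegol score. Arm A patients who did well on usual care would tend to lose their usual-care score. Both losses flatter naloxegol, so a period term cannot cancel them. A mixed model that keeps decliners' Day 18 scores reduces the bias but does not remove it, because the missingness may depend on the unobserved crossover score.

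At stake is the PAC-QOL comparison, one secondary measure. Scores not collected at the end of crossover cannot be recovered later.

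**Working it through.** The plan gives no calculation for PAC-QOL. Its only design calculation is for the primary endpoint (50 patients, 70% against 85%, one-sided exact test). That reproduces: success needs 41 of 50, exact alpha is 0.0402 and power is 0.791 against the stated 80%. Nothing below affects it.

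**Step 1. What each form recalls.** Inputs: initial period Days 1–14, washout Days 15–17, crossover Days 18–31 (Section 4.1 and Schedule of Events); 14-day recall (Section 5.1.13.6). A form on day *d* covers days *d* − 14 to *d* − 1.

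| Form | Days covered | Initial | Washout | Crossover |
|---|---|---|---|---|
| Day 18, nominal | 4–17 | 11 | 3 | 0 |
| Day 15, earliest in ±3 window | 1–14 | 14 | 0 | 0 |
| Day 21, latest in ±3 window | 7–20 | 8 | 3 | 3 |
| Day 32, extension only | 18–31 | 0 | 0 | 14 |
| End of Study, Day 31 + 21 = 52 | 38–51 | 0 | 0 | 0 |
| End of Study, Day 31 + 35 = 66 | 52–65 | 0 | 0 | 0 |

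At the ends of its own ±3-day window (Days 29 and 35), the Day 32 form recalls 11 crossover days.

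Under the within-28-days wording, the End of Study visit falls on Days 32–59. Overlap with crossover is 14 days at Day 32, 1 day at Day 45 and 0 from Day 46. So 14 of 28 possible days give any overlap, and one gives full overlap.

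These End of Study figures count from Day 31, because Sections 2.4 and 6.2 count both phases as study treatment. If the last naloxegol dose were meant, an Arm A decliner (last dose Day 14) would be seen on Days 35–49, with 11 down to 0 days of overlap.

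**Step 2. PAC-SYM.** With the 7-day recall of Section 5.1.13.5, Day 8 covers 7 initial days and Day 25 covers 7 crossover days, so that comparison is sound. Crossover week 2 (Days 25–31) is covered only by the extension's Day 32 form. Initial week 2 is weakly covered for everyone: Day 18 recalls 4 initial and 3 washout days. Appendix H prints a 2-week recall instead; on that wording the Day 25 form would mix 4 initial, 3 washout and 7 crossover days.

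**Step 3. How large the bias could be.** The documents give neither extension uptake nor its link to benefit, so this is an illustration with every input assumed. There is no true effect, 1:1 arms, and a random-intercept model with treatment and period. The period-2 score is missing for decliners and End of Study data are not used. A patient extends when a normal score, correlated 0.3 to 0.7 with that patient's naloxegol-minus-usual-care benefit, exceeds the uptake cut-off. The intraclass correlation is 0.3 to 0.7, with 1,000,000 simulated patients per cell. A linear model stands in for the planned ordinal one. Bias toward naloxegol is in SD of the within-patient difference. The count of patients without a form is 50 × (1 − uptake), if all 50 treated patients reach crossover.

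| Uptake | Patients without a form | Bias, two period scores | Bias, Day 1 added as an outcome row |
|---|---|---|---|
| 30% | 35 | 0.12–0.59 | 0.11–0.34 |
| 50% | 25 | 0.12–0.46 | 0.11–0.31 |
| 70% | 15 | 0.09–0.30 | 0.08–0.22 |
| 90% | 5 | 0.04–0.12 | 0.04–0.09 |

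At correlation 0 the bias is within 0.002 of zero in every cell. A different selection rule (the usual-care-minus-naloxegol difference plus noise of SD 0.5 to 2, within-patient correlation 0.5 or 0.7) gives the same direction, at 0.05 to 0.71 of the total SD. With the form completed by everyone at the end of crossover, the estimate is unbiased.

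**The case against.** The strongest reply is that this is probably an omitted table cell. Section 4.1 describes a visit that is not limited to extenders: "On Study Days 1, 18, 32, patients will undergo physical exam with vital signs and weight". Section 8.1.2 has patients bringing back diary and tablets "when they return to clinic every 14 days during the initial and crossover treatment phases". If staff follow Sections 4.1 and 5.1.13.6, the gap does not arise, and nothing in Sections 5.0 or 10.4 formally ranks the schedule above the text. All of that stands. But neither visit passage lists PAC-QOL, Section 5.3 repeats the omission, and the schedule is where staff are told to look.

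Second, the bias needs the Day 32 form to serve as the extenders' crossover value, and Section 9.3.3 does not say so. If it were excluded as an extension assessment, no patient would have a form recalling more than 3 of the 14 crossover days. The selective loss would disappear, but so would almost all the crossover information. The same fix closes that gap.

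Third, decliners do complete an End of Study form. When it was substituted in a simulation with a true effect of −0.5 SD, the estimate was −0.45 to −0.55. Two errors offset there: Arm B decliners are scored off naloxegol under a naloxegol label, while the selection remains. The near agreement need not hold for other effects, and under the schedule's timing the form recalls no crossover day.

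Fourth, patients may decline because of burden or illness, and the magnitudes rest wholly on assumptions. That stands, and the table should be read only as showing that the bias need not be negligible.

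**Conclusion.** The contradiction is certain: the text requires PAC-QOL every 14 days in both periods, and the Schedule of Events with Section 5.3 provides no end-of-crossover form for patients who decline the extension. The recall arithmetic follows from the documents on nominal dates.

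The bias is conditional. It needs staff to follow the schedule, the Day 32 form to be used as the crossover value, decliners' End of Study form not to be used, and extension choice to be related to individual benefit. Given those, the direction is toward naloxegol. The size cannot be fixed from the documents; the illustration spans 0.04 to 0.59 SD of the within-patient difference.

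The reach is limited to PAC-QOL and crossover week-2 PAC-SYM in a feasibility pilot. The primary endpoint, daily BPI-sf, the Day 8 against Day 25 PAC-SYM comparison (given 7-day recall) and the randomised Day 18 PAC-QOL comparison are not affected. It should be fixed, because the correction is cheap and the lost data are not recoverable.

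**What to change.** - Amend the Schedule of Events and Section 5.3 so that every patient completes PAC-QOL and PAC-SYM at the end of Day 14 and the end of Day 31. Tie both to the last treatment day of the period, before the extension decision, and send the forms home with the diary packet.
- In Section 9.3.3, name the Day 14 and Day 31 PAC-QOL as the period outcomes. Use the Day 14 and Day 31 PAC-SYM in addition to Days 8 and 25, not in their place. Exclude extension and End of Study values from the treatment comparison.
- Reconcile the PAC-QOL timing across Sections 4.1, 5.1.13.6, 5.3, 5.4.2 and 5.5 and the Schedule of Events. Also reconcile the two End of Study timings, and the PAC-SYM recall period (7 days in Section 5.1.13.5, 2 weeks in Appendix H).

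The cost is a protocol amendment and about 10 minutes of patient time at each of two time points (two questionnaires at about 5 minutes each, by Sections 5.1.13.5 and 5.1.13.6). There is no new visit and no change to the primary endpoint or sample size.

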5.5 End of Study Visit

The End of Study Visit will occur within 28 days of final day of study treatment. This visit will be scheduled at the time of a routine oncology visit. If physical exam, ECOG performance status, vitals, weight, and laboratory tests are performed at the End of Study timepoint as part of routine oncology care, results will be collected for the study.

- Documentation of adverse events and serious adverse events
- Naloxegol pill count and final study drug accountability
- PAC-SYM
- PAC-QOL
- BPI-sf
- Return of unused study materials, including study medication, patient questionnaires and diaries

5.6 Follow-up Procedures

Patients will be followed for occurrence of adverse events for 28 days after the final study treatment or until death, whichever occurs first. Patients removed from treatment for unacceptable adverse events will be followed until resolution or stabilization of the adverse event. There are no additional follow-up requirements beyond the end of study visit, as detailed in Section 5.5

6.0 Measurement of Effect

6.1 Safety/Tolerability

Analyses will be performed for all patients having received at least one dose of study drug. The study will use the NCI CTCAE v4.03 (<http://ctep.cancer.gov/reporting/ctc.html>) for reporting of adverse events. Safety will be assessed within the first 4 weeks of study treatment.

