2.2 Secondary Objectives

1. To determine the frequency of naloxegol versus usual care on OIC as defined by ≤ 3 bowel movements per week.
2. To evaluate naloxegol versus usual care on stool quality using the Bristol Stool Scale (BSS).²
3. To describe the adverse events associated with naloxegol when administered daily in this patient population and to compare the adverse events associated with Naloxegol with adverse events observed with usual care, using the National Cancer Institute Common Terminology Criteria for Adverse Events (NCI CTCAE) version 4.03.³
4. To evaluate health related quality of life utilizing the Patient Assessment of Constipation Symptoms (PAC-SYM)⁴ and Patient Assessment of Constipation Quality of Life (PAC-QOL).⁵
5. To evaluate changes in patient reported pain using the Brief Pain Inventory-Short Form (BPI-sf).⁶

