4.6 Adverse Drug Reactions, Dosing Delays/Dose Modifications

From initial treatment period to end of study visit, participants will be evaluated for possible toxicities that may have occurred during the previous treatment phase or drug dispensing cycle. Any patient who receives treatment on this protocol will be evaluable for toxicity. Severity of all adverse events will be evaluated according to the NCI CTCAE v4.03. Dose adjustments will be based on the naloxegol-related toxicity experienced during a treatment phase or newly encountered at the start of each treatment phase or drug dispensing cycle. Dose adjustments should be made according to the system showing the greatest degree of adverse event severity. If a patient experiences multiple adverse events and there are conflicting recommendations, the investigator should use the recommended dose adjustment

that reduces or delays the dose to the greatest degree. The participant may continue on therapy if the toxicity can be managed according to the dose modification guidelines as outlined below.

A separate 12.5 mg tablet will be available for study participants who develop more severe GI adverse events. For study drug compliance the pharmacy will indicate the date, dosage and quantity of drug dispensed. The subject will also maintain a the patient study drug diary (see sections 5.1.13.1 and section 8.1.2) that will be reviewed along with study drug counts to ensure that all missed doses or dose changes have been documented.

Patients requiring a delay of ≥ 2 weeks in initiation of study participation or requiring more than 2 dose adjustments during the course of naloxegol therapy will require authorization from the principal investigator to continue study participation.

Table 1: Dose Modifications for Naloxegol-Related Nausea and/or Vomiting

Vomiting	Management for Naloxegol
\leq Grade 1	No action required.
Grade 2	Hold until \leq Grade 1. Resume at same dose level.
Grade 3	Hold until $<$ Grade 2. Resume at reduced dose (12.5mg tablet).
Grade 4	Off protocol therapy
Recommended management: Dopamine antagonist antiemetic	

Table 2: Dose Modifications for Naloxegol-Related Diarrhea

Diarrhea	Management for Naloxegol
\leq Grade 1	No action required.
Grade 2	Hold until \leq Grade 1. Resume at same dose level.
Grade 3	Hold until $<$ Grade 2. Resume at reduced dose (12.5mg tablet).
Grade 4	Off protocol therapy

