5.1.13.1 Patient Study Drug Diary

Patients will complete a daily study drug diary (**Appendix D**) during the period of time that they are receiving naloxegol: initial treatment phase for patients randomized to Arm A, crossover treatment phase for those randomized to Arm B; extension phase for all patients who choose to continue receiving naloxegol for an additional 12 weeks following the crossover phase. Participants will be asked to complete this diary even on days when a naloxegol dose was missed. The study drug diary will be reviewed with the patient during each visit to clinic, and a copy will be collected by a member of the study team. This diary will be used in combination with a pill count by the study team to support drug accountability.

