8.0 AGENT INFORMATION

8.1 Naloxegol

Please refer to Investigator’s Brochure for more comprehensive information. IDS will be responsible for all naloxegol storage, preparation, accountability, and dispensing throughout the trial.

Other names for the drug: MOVANTIK™

Mechanism of action (or Product description): Naloxegol is an antagonist of opioid binding at the mu-opioid receptor. At recommended dose levels, naloxegol functions as a PAMORA (Peripherally Acting Mu-Opioid Receptor Antagonist) in tissues such as the bowel, thereby decreasing the constipating effects of opioids. Naloxegol is a PEGylated derivative of naloxone, and a substrate for the P-gp. The presence of the PEG moiety in naloxegol reduces its passive permeability as compared with naloxone. Due to the reduced permeability and increased efflux of naloxegol across the blood-brain barrier, related to P-gp substrate properties, the central nervous system penetration of naloxegol is negligible at recommended dose levels, limiting the potential for interference with centrally mediated opioid analgesia.

Availability: provided by AstraZeneca, free of charge

How supplied: Study drug tablets are supplied as mauve, oval, biconvex, film coated, and intagliated with “nGL” on one side and “25” on the other.

Tablets will be supplied in 25-mg dose form, in high-density polyethylene (HDPE) bottles. IDS will dispense a 14-day supply of naloxegol at the initiation of the initial treatment phase for those patients randomized to Arm A. For patients randomized to Arm B, IDS will dispense a 14-day supply of naloxegol at the initiation of the crossover treatment phase. Patients who choose to participate in the optional extension portion of the study will receive a 28-day supply every 4 weeks during the extension phase.

Naloxegol will be packaged and labeled by AstraZeneca. It will be clearly marked according to national requirements regarding use for clinical trial investigation only and will be labeled with drug name, study reference number, and storage conditions.

Storage and stability: Naloxegol will be stored and locked in a secure location within IDS, with access restricted to pharmacy personnel only. All study drug will be stored in original containers until dispensed to study subjects. Naloxegol must be stored at room temperature between 20-25C (68-77F). Excursions are permitted to 15-30C (59-86F). Storage temperature will be

monitored

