9.3.2 Safety Endpoint

Safety endpoints will be evaluated by monitoring AEs from clinical and laboratory reporting. Adverse events will be classified according to the NCI-CTCAE version 4.03. Trends in the distribution and severity of the AEs across the study groups will be assessed by examining the count of total AEs and count of AEs at each severity level over the course of the 2 weeks for the initial treatment and over the 2 weeks of the crossover treatment phases of the study.

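### Section 6.1 ties the safety analysis to a dose of an undefined 'study drug'; if that means naloxegol, Arm B patients who leave during usual care or washout are dropped and their Arm A counterparts are kept

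*Combined protocol and SAP*

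**What the plan says.** Section 6.1 (Safety/Tolerability) sets the safety population: "Analyses will be performed for all patients having received at least one dose of study drug". Section 4.6 gives a rule of its own: "Any patient who receives treatment on this protocol will be evaluable for toxicity". Secondary objective 3 in Section 2.2 is comparative, since part of it is "to compare the adverse events associated with Naloxegol with adverse events observed with usual care". Section 9.3.2 describes the analysis: trends across the study groups are "assessed by examining the count of total AEs and count of AEs at each severity level", separately for the initial and crossover periods. It names no analysis set.

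The term *study drug* has no definition. Section 8.1 describes the naloxegol product with the words "Study drug tablets are supplied as mauve, oval, biconvex, film coated". Section 8.1.2 states "Subjects will be asked to fill out a daily study drug diary while taking naloxegol", and Sections 4.2 and 5.1.13.1 likewise confine the study drug diary to the time on naloxegol. Sections 2.4, 4.1, 6.2 and 9.2, by contrast, define feasibility as completing the study drug or drugs across both the initial and the crossover phase.

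**The concern.** Arm A takes naloxegol from Day 1. Arm B has usual care on Days 1 to 14 and a washout on Days 15 to 17, and first takes naloxegol on Day 18 (Sections 4.2 and 5.3.1). If a dose of study drug means a dose of naloxegol, every Arm A patient who starts treatment enters the safety set at once, while an Arm B patient enters only by reaching Day 18. The patients lost are those who left on or just after usual care, possibly because of an event on it. Naloxegol has no matching loss.

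The comparison in objective 3 would then rest on a usual-care side with its early leavers removed and a naloxegol side with its early leavers kept. Because two sections support different populations, an analyst could also choose between them after seeing the data.

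**Working it through.** **1. The plan's own figure.** Section 9.2 gives n = 50, null 70%, alternative 85%, one-sided exact test at 0.05, power 80%. The smallest r with P(X ≥ r | 50, 0.70) ≤ 0.05 is 41 (size 0.0402; at 40 it is 0.0789). Power is P(X ≥ 41 | 50, 0.85) = 0.791, which agrees with the stated 80% to within a point. Section 9.2 keeps everyone who starts study treatment in the primary analysis, so the safety set does not affect this result.

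**2. What study drug covers.**

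| Where | Use of the term |
|---|---|
| 4.2, 5.1.13.1, 8.1.2 | The diary is kept only while on naloxegol |
| 8.1 | The tablets described are naloxegol |
| 2.4, 4.1, 6.2, 9.2 | Completion over both phases, though each patient has naloxegol in only one |
| 6.1, last sentence | Switches to the wider term *study treatment* |

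The usage is mixed, so both readings must be followed through.

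**3. Two patients who leave before Day 18.**

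| Patient | 6.1, naloxegol reading | 6.1, broad reading | 4.6 |
|---|---|---|---|
| Arm A, started naloxegol | In | In | In |
| Arm B, started usual care | Out | In | In |

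Sections 6.1 and 4.6 disagree in one cell, and only on the naloxegol reading.

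**4. How many.** Dropped Arm B patients = n × w × s, where n is the Arm B patients who start, w the proportion who withdraw, and s the share of withdrawals that fall before crossover. Take n = 50/2 = 25, from the 1:1 allocation. The documents give neither w nor s. As assumptions, w runs from 15% to 30% (one minus the alternative and null completion rates) and s from 50% to 100%.

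| w | s | Arm B dropped | Arm A dropped | Safety set, of 50 |
|---|---|---|---|---|
| 15% | 50% | 25 × 0.15 × 0.5 = 1.88 | 0 | 48.12 |
| 15% | 100% | 25 × 0.15 × 1 = 3.75 | 0 | 46.25 |
| 30% | 50% | 25 × 0.30 × 0.5 = 3.75 | 0 | 46.25 |
| 30% | 100% | 25 × 0.30 × 1 = 7.50 | 0 | 42.50 |

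A constant stopping rate per period gives nearly the same lower figure: 1 − √0.85 = 0.078, and 25 × 0.078 = 1.95.

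**5. Direction.** The dropped patients never took naloxegol. Removing them leaves the naloxegol event count as it was, and lowers the usual-care count or leaves it unchanged. This holds for counts. For a proportion or a rate the denominator falls too, so the direction depends on whether those dropped had more events than those kept.

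**6. Illustration with invented risks.** Suppose there is no true difference, a 30% chance of an event per period among those who stay, and an event in every patient who leaves before crossover. With w = 15% and s = 50%, 7.5% of each arm leaves early. The naloxegol proportion is (25 × 0.925 × 0.30 + 25 × 0.075 + 25 × 0.925 × 0.30) / (25 + 25 × 0.925) = 15.75/48.125 = 32.7%. Usual care would also show 32.7% with everyone kept, but shows 30% on the naloxegol reading of Section 6.1. With w = 30% and s = 100%, the figures are 18/42.5 = 42.4% and 30%. Giving every early leaver an event makes this close to a worst case.

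**The case against.** The strongest reply is that study drug need not mean naloxegol. Section 6.2, directly after 6.1, applies the term to both phases, as do Sections 2.4, 4.1 and 9.2. Section 9.3.4 plans to compare weekly pill counts between naloxegol and usual care, and Section 4.1 has patients receive a new treatment supply on Days 1, 18 and 32 without limiting this by arm. On that reading Sections 6.1 and 4.6 agree. This stands, and it makes the exclusion conditional. It does not say which reading governs Section 6.1.

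It can also be said that Section 4.6 already supplies an inclusive rule, that events are collected in both arms throughout, and that the data and safety monitoring board sees all adverse events regardless of grade and attribution (Section 10.6). So this is a defect of the analysis set and not a gap in data or oversight. But being evaluable under Section 4.6 does not override an explicit restriction in Section 6.1, and Section 9.2.1 adds a third rule for secondary endpoints (baseline and follow-up data required), among which Section 9.3.3 lists adverse events.

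On raw counts, Section 2.4 names a rate as the safety endpoint and Section 9.3.3 plans mixed models for the secondary variables, so it would be too strong to say that the plan offers nothing but counts. However, Section 9.3.3 specifies no model form for adverse events, and Section 9.3.2 gives no denominator.

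Finally, the 15% figure concerns completion of study drug. A patient who misses doses may still cross over and take naloxegol, and would not be dropped. That is why the sizes above are assumptions.

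**Conclusion.** The point holds in conditional form. Section 6.1 uses an undefined term with two usages in the same document. On the one found in the diary, supply and accountability text, the safety set loses Arm B early leavers only and conflicts with Section 4.6; on the other, nobody is lost. If the naloxegol reading is applied, about 2 of 25 Arm B patients are lost under 15% withdrawal split evenly over the periods, and about 2 to 7.5 over the wider range. The proportion withdrawing and its timing are assumed.

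Three stronger conclusions are tempting but unsupported:

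- A reader might infer that Section 6.1 flatly contradicts Section 4.6. It does so only on one reading.
- A reader might infer that the plan makes naloxegol look worse than it is. That needs the narrow reading and events among the patients dropped, and neither is established.
- A reader might infer that about half of the usual-care events leading to withdrawal would vanish. With 7.8% stopping per period, Arm B's first period does hold 1.95/(1.95 + 1.80) = 52% of usual-care withdrawals, where 1.80 is 0.078 × 23.05 Arm A patients who cross over. But that is a share of assumed withdrawals; no event rate or reason for leaving enters it.

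The matter should still be settled before analysis, because objective 3 depends on it and the correction is cheap. The primary endpoint and its power are not affected.

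**What to change.** Replace the sentence in Section 6.1 with: *The safety analysis includes all randomised patients who started either assigned treatment (naloxegol or usual care), with events attributed to the treatment being taken.* This agrees with Section 4.6. Refer to the same set in Section 9.3.2, and state there how events starting in the washout are counted, since no assigned treatment is scheduled on Days 15 to 17.

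In Section 9.3.2 and the synopsis, report the number of patients with an event and the events per patient-day on each treatment beside the raw counts. This brings the analysis into line with the rate named in Section 2.4 and allows for unequal exposure when patients stop early.

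The cost is about two sentences and slightly more tabulation. Event dates and therapy start and stop dates are already on the adverse event form (Section 7.6.4), and the medication use diary runs through both treatment periods. No patients, visits or procedures are added.
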